Section to be changed Description of change	After the interim data base lock, frequency of tumor assessment may be adapted according to local standard of care and in agreement with the sponsor if the patient is deriving clinical benefit (e.g. CR, PR or SD > 6 months). To reduce imaging assessment frequency 5.2 assessment of efficacy Was added: After the interim data base lock, collection of tumor markers in the e-CRF is no longer required. Following data the interim data base lock there is no longer requirement to enter tumor maker data in e-CRF Abbreviation and section 5.3.6.1 Definition of AEs	

Trial Protocol

Section to be changed	6.2 - Details of trial procedures at selected visits	
Description of change	Was added:	
Description of change	After the interim data base lock, mandatory	
	procedures/assessments and documentation in the	
	eCRF will be adapted as described in the flow chart	
	and the respective sections of this protocol	
Rationale for change	To reflect the changes to trial procedures/assessments	
	following the interim data base lock	
Section to be changed	6.2.2 treatment period(s)	
g	6.2.3.3 Follow-up period for progression	
Description of change	Was added:	
F	After the interim data base lock, frequency of tumor	
	assessment may be adapted according to local	
	standard of care and in agreement with the sponsor	
	if the patient is deriving clinical benefit (e.g. CR, PR	
	or SD > 6 months).	
Rationale for change	To reduce imaging assessment frequency	
Section to be changed	Section 6.2.3.5 trial completion	
Description of change	Section 6.2.3.5 was added:	
•	The clinical trial will be considered completed when	
	the last patient has completed the EoR visit.	
	If patients are still on treatment at the time of	
	interim data base lock and the Clinical Trial Report	
	is written, these patients will be maintained in the	
	trial as long as they are deriving clinical benefit (i.e.	
	no disease progression, no drug-related AEs	
	requiring drug discontinuation) or no new anti-	
	cancer treatment started and there are willing to	
	continue. For these patients, no blood sample will be	
	collected for PK/PD and biomarker analysis, only	
	(S)AEs and limited efficacy data will be collected.	
	After the discontinuation of these patients,	
	additional data collected after interim data base	
	lock will be reported in separate listings and will not	
	lead to any further update of tables generated for	
	lead to any further update of tables generated for	
Rationale for change	lead to any further update of tables generated for section 15 of the CTR unless deemed necessary.	
Rationale for change	lead to any further update of tables generated for section 15 of the CTR unless deemed necessary. These listings will be included in a revised CTR.	
Rationale for change Section to be changed	lead to any further update of tables generated for section 15 of the CTR unless deemed necessary. These listings will be included in a revised CTR. Clarification for the definition of trial completion	
	lead to any further update of tables generated for section 15 of the CTR unless deemed necessary. These listings will be included in a revised CTR. Clarification for the definition of trial completion following the interim data base lock	
Section to be changed	lead to any further update of tables generated for section 15 of the CTR unless deemed necessary. These listings will be included in a revised CTR. Clarification for the definition of trial completion following the interim data base lock Section 7.7 determination of sample size	
Section to be changed	lead to any further update of tables generated for section 15 of the CTR unless deemed necessary. These listings will be included in a revised CTR. Clarification for the definition of trial completion following the interim data base lock Section 7.7 determination of sample size Was deleted	
Section to be changed	lead to any further update of tables generated for section 15 of the CTR unless deemed necessary. These listings will be included in a revised CTR. Clarification for the definition of trial completion following the interim data base lock Section 7.7 determination of sample size Was deleted Additional 10-15 patients will be included in the	

Trial Protocol

Rationale for change	Expansion cohort is no longer planned for this trial	
Section to be changed	8.6 End of Trial	
Description of change	The trial will end when the last patient has completed	
_	the last follow up visit as specified in Section 6.2.3.4	
	Was changed to:	
	After the interim data base lock the trial will end	
	when the last patient has completed the EoR visit as	
	specified in Section 6.2.3.4 and 6.2.3.5	
Rationale for change	Clarification for the definition of end of trial, following	
	the interim data base lock	

APPROVAL / SIGNATURE PAGE

Document Number: c03124055 Technical Version Number: 6.0

Document Name: clinical-trial-protocol-version-04

2. LIST OF ABBREVIATIONS

Include a list of all abbreviations used in the TSAP

| Term | Definition / description | | | |
|---|--|--|--|--|
| ADA | Anti-Drug Antibodies | | | |
| AP | Alkaline Phosphatase | | | |
| ALT | Alanine Aminotransferase | | | |
| AST | Aspartate Aminotransferase | | | |
| aPTT | Activated Partial Thromboplastin Time | | | |
| AE | Adverse Event | | | |
| AUC | Area Under the Curve | | | |
| AUEC | Area under the effect curve | | | |
| BLRM Bayesian Logistic Regression Model | | | | |
| BSA | Body Surface Area | | | |
| BMI | Body Mass Index | | | |
| BRPM | Blinded Report Planning Meeting | | | |
| CRF | Case Report Form | | | |
| CTC Common Terminology Criteria | | | | |
| CTP Clinical Trial Protocol | | | | |
| CTR | Clinical Trial Report | | | |
| DCE-MRI | Dynamic Contrast-Enhanced Magnetic Resonance Imaging | | | |
| DLT | Dose Limiting Toxicity | | | |
| DM&SM | Boehringer Ingelheim Data Management and Statistics Manual | | | |
| DRA | Drug Regulatory Affairs | | | |
| DMG | Dictionary Maintenance Group | | | |
| DSB | Data Safety Board | | | |
| eCRF | Electronic Case Report Form | | | |
| EMEA | European Agency for the Evaluation of Medicinal Products | | | |
| FAS | Full Analysis Set | | | |
| $IAUC_{60}$ | Initial area under contrast agent concentration—time curve at 60 s | | | |
| ICH | International Conference on Harmonisation | | | |
| INR | International Normalised Ratio | | | |
| Ktrans | Volume transfer constant obtained from DCE-MRI data | | | |
| LOCF | Last Observation Carried Forward | | | |

TSAP for BI Trial No: 1336.6 Page 5 of 23
Proprietary confidential information © 2017 Boehringer Ingelheim International GmbH or one or more of its affiliated companies

| Term | Definition / description | | | |
|--------|--|--|--|--|
| MedDRA | Medical Dictionary for Regulatory Activities | | | |
| MQRM | Medical Quality Review Meeting | | | |
| MTD | Maximum Tolerated Dose | | | |
| O*C | Oracle Clinical | | | |
| PK | Pharmacokinetics | | | |
| PLT | Platelets | | | |
| PPS | Per Protocol Set | | | |
| PSTAT | Project Statistician | | | |
| PT | Prothrombin Time | | | |
| PT | Preferred Term | | | |
| PV | Protocol Violation | | | |
| Q1 | Lower Quartile | | | |
| Q3 | Upper Quartile | | | |
| RECIST | Response Evaluation Criteria In Solid Tumors | | | |
| REP | Residual Effect Period | | | |
| SA | Statistical Analysis | | | |
| SD | Standard Deviation | | | |
| SMQ | Standardised Meddra Query | | | |
| SOC | System Organ Class | | | |
| TCM | Trial Clinical Monitor | | | |
| TESS | Treatment Emergent Signs And Symptoms | | | |
| ToC | Table Of Contents | | | |
| TMW | Trial Medical Writer | | | |
| TSAP | Trial Statistical Analysis Plan | | | |
| WBC | White Blood Cell Count | | | |

3. INTRODUCTION

As per ICH E9 (1), the purpose of this document is to provide a more technical and detailed elaboration of the principal features of the analysis described in the protocol, and to include detailed procedures for executing the statistical analysis of the primary and secondary variables and other data.

This Trial Statistical Analysis Plan (TSAP) assumes familiarity with the Clinical Trial Protocol (CTP), including Protocol Amendments. In particular, the TSAP is based on the planned analysis specification as written in CTP Section 7 "Statistical Methods and Determination of Sample Size". Therefore, TSAP readers may consult the CTP for more background information on the study, e.g., on study objectives, study design and population, treatments, definition of measurements and variables, planning of sample size, randomization.

SAS® Version 9.4 will be used for all analyses.

4. CHANGES IN THE PLANNED ANALYSIS OF THE STUDY

Section 7.3.5.3 of the CTP stated that "The exploratory statistical analyses of the biomarker data will be performed separately and results will be covered in a separate report." However, the team has now decided to include the biomarker analyses as a part of CTR and section 5.4.1 and section 9 of this TSAP covers a list of the biomarkers to be analyzed and section 7.8.5 provides further details on their analysis.

TSAP for BI Trial No: 1336.6

Proprietary confidential information © 2017 Boehringer Ingelheim International GmbH or one or more of its affiliated companies

5. ENDPOINT(S)

5.1 PRIMARY ENDPOINT(S)

The objective of this study is to determine the safety and tolerability of BI 836880. The primary endpoint is the determination of the maximum tolerated dose (MTD) of BI 836880 based on the number of patients with dose-limiting toxicities (DLTs) during the first treatment cycle. The DLT is defined in section 5.3 of the CTP.

The MTD is defined as the highest dose with less than 25% risk of the true DLT probability being above 33%, and may be considered reached if the probability that the true DLT rate is in target interval (16%-33%) is sufficiently large during the MTD evaluation period.

The MTD evaluation period is defined as the time within 3 weeks after first administration of study treatment.

Patients who have not completed one cycle of treatment will be replaced. Patients who were replaced during the MTD evaluation period will not be considered for MTD determination. Those patients that have completed the MTD evaluation period without having been replaced will be referred to as patients evaluable for MTD.

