3. DESCRIPTION OF DESIGN AND TRIAL POPULATION

3.1 OVERALL TRIAL DESIGN AND PLAN

This is a Phase I, multi-centre, non-randomized, uncontrolled, open-label, dose escalating study of BI 836880 administered intravenously. The eligible patient population will be patients with advanced solid tumors. Dose escalation will be guided by a Bayesian logistic regression model with over dose control (details refer to Section 7), restricted to a maximum 200% dose increment for the first dose escalation and maximum of 100% dose increment for dose \geq 120 mg. At any time during the trial, it will not be permitted to escalate to a dose which does not fulfil the escalation with overdose control (EWOC) criterion (refer to Section 7).

For any dose-escalation cohort, at least 2 patients will be required. At first dose level, first patient will be treated and observed for at least 2 weeks before allowing the second patient to receive BI 836880 infusion. For subsequent dose levels within dose escalation, each patient in a given cohort (dose level) will be observed for a minimum of 48 hours after first BI 836880 application before allowing treatment for subsequent patient in the same cohort.

In case only 2 patients are evaluable and neither has experienced a DLT within the first course, then dose-escalation can occur based on these 2 patients. However, should one of these 2 patients experience a DLT in the first course, a third patient will be enrolled at the same dose level. After all patients in a cohort have either experienced a DLT or have been observed for at least one course (3 weeks) without a DLT, the Bayesian model will be updated with the newly accumulated data. The overdose risk will then be calculated for each dose, and escalation will be permitted to all doses which fulfil the EWOC criterion and the dose escalation scheme according to Section 4.1.3. Decision on further recruitment (dose escalation, de-escalation or cohort expansion) will be made by a Data Safety Board (DSB) based on the collected safety data as well as other data (e.g. PK/PD data) when available.

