6.3 PATIENT SETS ANALYSED

Treated set

This patient set includes all patients enrolled in the trial who were documented to have taken at least one dose of study medication.

Dose finding cohort treated set:

This patient set includes all patients enrolled in dose finding and confirmation of MTD cohort of the trial who were documented to have taken at least one dose of study medication and were evaluable for the MTD determination.

MTD Expansion cohort treated set:

This patient set includes all patients enrolled in expansion cohort of the trial who were documented to have taken at least one dose of study medication.

Tumor type expansion treated cohort set

This patient set includes all patients with selected tumor type enrolled in expansion cohort of the trial who were documented to have taken at least one dose of study medication.

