7.4 PRIMARY ENDPOINT(S)

The primary endpoint is to assess the MTD based on the number of patients presenting DLTs during the MTD evaluation period. The primary analysis is for the determination of the MTD. The purpose of this analysis is to summarize and document the data that led to the selection of the MTD. Therefore, an overall summary of DLTs (see CTP section 5.3.1 for the definition of DLTs) which occurred during the MTD evaluation period will be provided for each dose cohort from the dose finding cohort treated set. Patients, if any, who did not complete the MTD evaluation period for reasons other than DLT will be excluded from the analysis of the primary endpoint.

A summary of the number of patients with DLTs overall in any course will be also given by initial treatment and displayed in a similar format to the summary of DLTs occurring in the MTD evaluation period.

The analysis of the MTD is based on a Bayesian logistic regression model (BLRM) guided by the escalation with overdose control principle. The MTD is defined as the highest dose for a given schedule that is expected to cause less than 25% risk of the true DLT rate being above or equal to 33% during the MTD evaluation period. Estimation of the MTD during the dose escalation phase of the study will be based upon the estimation of the posterior probability of the incidence of DLT in toxicity categories during the MTD evaluation period for all evaluable patients. The model to be used is specified in CTP section 7.

The posterior probabilities that the toxicity rates of each dose level fall into the categories specified in CTP section 7 will be displayed.

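### SAP 5.1 defines who is evaluable for the MTD without an exception for DLT patients, so read literally a DLT can drop out of the final MTD analysis

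*SAP*

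**What the plan says.** SAP 5.1 sets the rule in three sentences:

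- The first covers replacement: "Patients who have not completed one cycle of treatment will be replaced".
- The second gives the consequence for the analysis: "Patients who were replaced during the MTD evaluation period will not be considered for MTD determination".
- The third fixes the term that the rest of the SAP uses: "Those patients that have completed the MTD evaluation period without having been replaced will be referred to as patients evaluable for MTD".

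None of the three has an exception for DLT or for related toxicity. Two later places use the term. SAP 6.3 limits the dose finding cohort treated set to patients "documented to have taken at least one dose of study medication and were evaluable for the MTD determination". SAP 7.4 takes the DLT summary from that set and estimates the "posterior probability of the incidence of DLT in toxicity categories during the MTD evaluation period for all evaluable patients".

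SAP 7.4 also has a different rule: only patients "who did not complete the MTD evaluation period for reasons other than DLT will be excluded from the analysis of the primary endpoint".

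The protocol agrees with that last sentence on DLTs. Protocol 3.1 updates the model once every patient in a cohort has "either experienced a DLT or have been observed for at least one course (3 weeks) without a DLT". Protocol 3.3.4.1 treats a patient with an incomplete first course as not evaluable, and replaces that patient, only when the reason is something other than toxicity related to the drug. Protocol 7.3 defines the primary analysis population by reference to 3.3.4.1. SAP 4 lists one change to the planned analysis, on biomarkers, so the SAP 5.1 rule is not declared as a departure.

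**The concern.** The patient that SAP 5.1 leaves out is one the design foresees. Protocol 4.1.4.2 requires drug to be stopped, at least temporarily, after a DLT, and protocol 3.3.4.1 lists a DLT without adequate recovery as a reason to withdraw treatment. An incomplete first cycle is a natural result of the event the primary endpoint counts.

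The MTD rests on a handful of DLTs, and leaving one out always lowers the estimated overdose probability, which favours a higher dose. SAP 7.4 gives the aim of the analysis: "The purpose of this analysis is to summarize and document the data that led to the selection of the MTD". An analysis set that omits a DLT the DSB acted on cannot do that.

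There is a second mismatch. A patient who stops in cycle 1 for a related toxicity short of a DLT is not replaced under protocol 3.3.4.1, but is excluded under SAP 7.4, because the reason is not a DLT.

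**Working it through.** **Text.** A patient has a DLT in cycle 1, stops drug and does not complete the cycle.

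| Place | Treatment of this patient |
|---|---|
| SAP 5.1 | replaced, not considered, not evaluable |
| SAP 6.3 | outside the dose finding set (inherits 5.1) |
| SAP 7.4, posterior | outside (evaluable patients only) |
| SAP 7.4, exclusion sentence | kept |
| Protocol 3.1 | counted once the DLT occurs |
| Protocol 3.3.4.1 and 7.3 | not replaced, kept |

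**Model (protocol 7.1).** logit p(d) = log α + β·log(d/1250). The prior on (log α, log β) is a three-part normal mixture with zero correlations:

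- weight 0.90, means (0.740, 0.798), SDs (2, 1)
- weight 0.05, means (0.846, −0.123), SDs (2, 1)
- weight 0.05, means (−2.731, 0.193), SDs (5, 0.01)

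The likelihood is binomial at each dose. The posterior was integrated numerically on an 801 × 801 grid per component. Overdose means p ≥ 0.33, and a dose passes if P(overdose) is under 0.25.

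**Reproducing the protocol's figures.** Computed against printed P(overdose):

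- Table 7.1:2 (prior): 240 mg 0.231 against 0.231; 480 mg 0.351 against 0.346; 960 mg 0.596 against 0.595.
- Table 10.6:1: scenario 4 at 120 mg 0.237 against 0.231; scenario 5 at 120 mg 0.629 against 0.623; scenario 7 at 480 mg 0.228 against 0.229; scenario 8 at 960 mg 0.339 against 0.353.

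The largest gap is 0.014.

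**Effect in the protocol's own table.** Scenario 4 is 0/2 at 40 mg and 1/3 at 120 mg, with printed P(overdose) 0.231 at 120 mg and a next dose of 120 mg. Remove the DLT patient and the data are scenario 3 (0/2, 0/2): printed 0.018 at 120 mg, next dose 240 mg at 0.066. This shows how much one DLT patient weighs. It is not an MTD declaration, since no DLT would remain and protocol 7.1 requires at least one.

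**Example A (assumed data).** 0/2 at 40 mg, 0/2 at 120 mg, 0/3 at 240 mg, 2/6 at 480 mg. Results at 480 mg:

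| Data at 480 mg | P(under) | P(target) | P(over) |
|---|---|---|---|
| 2/6, all counted | 0.274 | 0.443 | 0.282 |
| 1/5, one DLT patient dropped | 0.572 | 0.318 | 0.111 |
| 1/6, dropped and replaced without DLT | 0.631 | 0.293 | 0.077 |

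480 mg crosses the 25% limit. It is not yet a declarable MTD, because P(target) is below 0.50 and there are only 12 or 13 patients against the 18 that criterion 3 needs.

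**Example B (assumed data).** 0/2 at 40 mg, 0/2 at 120 mg, 0/9 at 240 mg, 3/7 at 480 mg.

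- All counted: P(over) is 0.351 at 480 mg, which fails, and 0.004 at 240 mg. 240 mg is the highest listed dose that passes. It meets criteria 1 and 3 with 3 DLTs, 2+2+9+7 = 20 patients and 9 at the dose.
- One DLT patient dropped (2/6): P(over) is 0.183 at 480 mg, which passes, and 0.646 at 720 mg, which fails. 480 mg meets criteria 1 and 3 with 2 DLTs, 2+2+9+6 = 19 patients and 6 at the dose.
- Dropped and replaced without DLT (2/7): P(over) is 0.136 at 480 mg.

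The escalation rules can produce these data: cohorts of 2, 2, 3, then 3 at 480 mg (1 DLT), 4 more at 480 mg (2 DLTs), then 6 at 240 mg. P(over) at 480 mg is 0.10 before it opens, 0.23 after 1/3 and 0.48 after 3/7, when 240 mg stands at 0.04.

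**The case against.** The strongest reply is that the literal reading is wider than practice would be. If replacement is run under protocol 3.3.4.1, a DLT patient is not replaced, so the SAP 5.1 sentence on replaced patients does not reach that patient. What remains is whether the patient completed the MTD evaluation period, which SAP 5.1 defines as a three-week window and not as doses received. A patient who stops drug but is observed for 21 days could be said to have completed it. Only DLT patients who leave observation sooner, through death or withdrawal of consent for example, would then be lost.

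Further, SAP 7.4 already has the right exclusion rule for DLT patients, and the SAP says it is based on protocol section 7. The DSB would already have acted on every DLT, so the likely outcome is a posterior that visibly disagrees with its record. The examples are constructed, and the replacement rows assume a DLT patient is actually replaced, which the protocol does not do.

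Much of this stands, and it bounds the size. It does not remove the defect. The first sentence of SAP 5.1 asks for a completed cycle of treatment, not a completed observation window, and leaves completion undefined. Nothing says whether the definition in 5.1 or the sentence in 7.4 prevails. Even the narrow reading loses some DLT patients, including any who die before day 21. Giving 7.4 priority also leaves open how related toxicity short of a DLT is handled.

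**Conclusion.** The concern holds and should be fixed. As written, SAP 5.1, carried into SAP 6.3 and the SAP 7.4 posterior, conflicts with SAP 7.4's own exclusion sentence and with protocol 3.1, 3.3.4.1 and 7.3.

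In the assumed examples, losing one DLT patient takes P(overdose) at 480 mg from 0.28 to 0.11 (A) or from 0.35 to 0.18 (B). In B, the dose meeting the protocol 7.1 criteria rises from 240 to 480 mg. These sizes rest on assumed data, the protocol prior, one DLT patient lost, and the literal SAP 5.1 rule applied to the final set. Under SAP 7.4 and the protocol the shift is zero. The documents give no rate for DLT patients with an incomplete first cycle, so no overall probability of error is claimed. Live dose escalation is not affected.

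**What to change.** Use one definition in SAP 5.1, 6.3 and 7.4: a treated patient is evaluable for the MTD if a DLT occurred in the MTD evaluation period, whether or not the cycle was completed, or if the patient completed the first course as protocol 3.3.4.1 requires without a DLT.

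Limit the replacement sentence in SAP 5.1 to the non-completers whom protocol 3.3.4.1 replaces, and state what completing the cycle means when infusions are skipped. Reconcile protocol 3.3.4.1 (related toxicity) with SAP 7.4 (DLT), and state how patients who stop for related toxicity short of a DLT enter the analysis.

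The cost is SAP wording only, with no extra patients or procedures.

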5.2 SECONDARY ENDPOINT(S)

5.2.1 Key secondary endpoint(s)

There were no key secondary endpoints for this study.

5.2.2 (Other) Secondary endpoint(s)

The following secondary endpoints related to safety and PK, were specified:

• Drug related AEs leading to dose reduction or discontinuation during the treatment period

TSAP for BI Trial No: 1336.6 Page 9 of 23
Proprietary confidential information © 2017 Boehringer Ingelheim International GmbH or one or more of its affiliated companies

